We propose an RCT that will assess the effects of EFT on medication adherence, general PM, and DD among those with pre- or type 2 diabetes or related comorbidities who are currently taking at least one oral medication for diabetes or related comorbidities. We will recruit participants who are relatively non-adherent to an oral medication ($\leq 80\%$ of prescribed doses taken in the past month; to accommodate over-reporting) for prediabetes or type 2 diabetes or other conditions that commonly co-occur with these conditions (e.g., hypertension, hyperlipidemia). Medication adherence will be monitored using electronic pill bottle caps (MEMS caps, which record bottle openings with date and time stamps), pill counts, and pharmacy records. Medications for glucose control as well as control of hypertension and/or hyperlipidemia will be considered as targets for measurement. Participants self-rated as non-adherent ($\leq 80\%$ prescribed doses taken), and report difficulty remembering to take one’s medication as a primary reason for non-adherence, will undergo a 6 week, 8 week, or 10 week baseline period. After the staggered baseline periods, all participants will receive EFT intervention. In total, participants will be in baseline and treatment for a total of 15 weeks.

Randomized participants will complete bi-weekly in person sessions plus phone sessions for the weeks in which they do not come to the lab, in which they learn to engage in EFT for medication adherence. Initial EFT for medication adherence will focus on taking the targeted medication on a typical day (e.g., a weekday when the participant usually works), and in subsequent sessions EFT will be used to assist participants in adapting to unusual circumstances that may interrupt adherence or have been reported as contributing to non-adherence.

At an initial baseline session, post-intervention, and follow-up, participants will complete measures of working memory, lab-based PM, and DD. Dependent measures include change in targeted medication adherence (based on MEMS data), change in non-targeted medication adherence (for participants initially reporting non-adherence to multiple medications; based on self-report and pill count measures), DD, and PM. Moderators to be tested include working. The goal of the study will be to collect pilot data to test the feasibility and initial efficacy of the approach, as well as effect sizes for a subsequent R01.

4.2 Include complete citations or references.

Response:

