5.0 Study Design*

5.1 *Describe and explain the study design (e.g. case-control, cross-sectional, ethnographic, experimental, interventional, longitudinal, observational).*

Response:

This study is a nonconcurrent multiple baseline design; participants will be randomized to a 6 week, 8 week, or 10 week staggered baseline periods followed by 4-8 weeks of Episodic Future Thinking (EFT).

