All participants complete a 6-week baseline in which they will use the MEMS bottles. At week 6, all participants will attend an in-person lab session to assess their adherence levels through looking at data from the MEMS bottles and pill counts.

Covid-19 Alternative Procedure: All participants will complete a 6-week baseline in which they will use the MEMS bottles. At week 6, data from the MEMS bottle will be obtained. In order to reduce participant and staff interaction due to COVID-19, this procedure will involve participants placing the cap from the MEMS bottle in a small bag placed in their mailbox. Research staff will conduct mobile data collection, and simply pick up the MEMS cap, and using sanitation

procedures, remotely download the data from the MEMS cap. The cap will then be returned to the participants mailbox.

Participants will then be randomly assigned to either the 6-week, 8- week or 10-week baseline. If a participant's medication adherence is not below 80%, they will be asked to come in at week 8 to reassess their adherence level (similarly, if their adherence is not below 80% at week 8, they will be asked to come back at week 10. If their adherence is not below 80% at this point, they will be dismissed from the study). If a participant is below 80% adherence within this 6-week period and their adherence is stable, meaning that there is no increasing trend in their adherence level, they will be randomly assigned to either a 6-week, 8- week or 10-week baseline. Participants who were assigned 6- week baseline, will now be eligible to start the intervention, those in the 8-week will complete two more weeks of baseline prior to the intervention, and those in the 10-week will complete four more weeks of baseline prior to the intervention *.

*Participants must be considered stable based on their pill counts to continue to the intervention period. For this study stability will be defined as no increasing trend (3 data points) in their adherence level. If a participant was assigned to a group but is not stable during that time period, they will be assigned to the next group (if disqualified for 6-week they will go to the 8-week and so on).

Assessment Sessions:

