Participants will complete the major life events assessment and a variety of assessments pertaining to executive function/memory. Similar to the screening/baseline session, these measures will all be administered via Zoom. Some of these tasks may only be administered in certain assessment sessions (e.g., the initial and/or final).

The types of tasks participants may complete are:

- Prospective memory tasks
- A working memory task
- An impulsive choice task

Participants will also have their height/weight taken, and the research staff will obtain self-report and objective measures of medication adherence (e.g., information such as data from MEMS caps, pill counts, reasons for non-adherence, and reasons for opening medication bottles).

Intervention Sessions:

During the Covid-19 Quarantine All intervention sessions will be conducted via zoom.

During each intervention meeting, the research staff will obtain self-report and objective measures of medication adherence, and participants will either complete EFT or IC activities, dependent on group assignment. Pill counts and MEMS data may be obtained by a staff member that is not acting as the interventionist for EFT/IC activities, so as to reduce the total time the participant must be in the lab.

Participants assigned to EFT will be asked to generate episodic cues, similar to the tasks used in our previous studies on EFT's effect (Daniel et al., 2013); unlike in prior studies, however, cues will be specific to instances of taking one's medication and/or positive events resulting from successful medication adherence. The episodic component of the thinking task occurs while the participants are asked to describe the perceptual details of the medication-taking (e.g., taking medication at home on a typical day, or while out of town on vacation) or medication-outcome event (feeling better and more energetic after medication, etc.). Participants will be asked open-ended questions to prompt more detail (such as what they are seeing, hearing, smelling, feeling), and to identify what successful adherence may look like if the initial event description does not go as planned (e.g., if you normally take your medication when you make coffee, what would successfully taking your medication look like on a day when you run out of time to make it?). Participants may record their EFT events into audio cues, so that they can practice using EFT using different modalities at home.

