Participants assigned to IC will be asked to generate cues about newly-learned health information. For this activity, the research staff will provide participants with a weekly learning module that will consist of presenting information on relevant health-related topics (e.g., information about diagnosed conditions that made them eligible for participation), which may include brief quizzes, informational videos, and other learning-oriented activities that may help with information retention (e.g., playing a memory game incorporating information about glucose metabolism). Participants will be asked to generate cues about the course content which may include imagining different ways the information could be useful, how it could be applied in different contexts, with different people, etc. As in EFT, participants will be asked open-ended questions as needed to prompt more details, and IC participants may also audio record their cues.

Participants will be asked to rate their cues on different dimensions (e.g., vividness, usefulness, valence, salience), which will be used to calculate a richness score (average of dimension ratings).

EFT participants may be provided the same information that IC participants are provided, to ensure both groups are equally knowledgeable on the topics; this information may be provided in a different format for ease of use/reference outside of the laboratory (e.g., on a study website, pamphlet, or booklet).

Participants will be trained to use EFT/IC outside of the lab using the ecological momentary intervention (EMI) computer based program that we have developed: the Mobile Audio Management and Response Tracker (MAMRT). This program, which is part of the study website, can be accessed by smartphone, tablet or computer. This application stores participants' EFT/IC cues, prompts their use (e.g., reminder text message, reminder email), asks questions about use of their cues, and records their use. Participants will be instructed to practice using EFT/IC daily. The MAMRT software was previously approved in STUDY00000936, and appears in Sze, Daniel, Kilanowski, Collins, and Epstein, 2015. In addition to the above, the MAMRT website may also be used to provide health information (i.e., that provided to the IC group), and other activities such as

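### Leftover two-group text lets EFT participants receive the IC group's health information; in the all-EFT design that material would start with EFT and could not be separated from it

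*Combined protocol and SAP*

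**What the plan says.** **The permission.** Section 12.1, under Intervention Sessions, states that "EFT participants may be provided the same information that IC participants are provided, to ensure both groups are equally knowledgeable on the topics". It adds that "this information may be provided in a different format for ease of use/reference outside of the laboratory", naming a study website, pamphlet or booklet. A second clause in the same section says that "the MAMRT website may also be used to provide health information (i.e., that provided to the IC group"), and allows quizzes on the educational material there. Both provisions are optional. Neither says who gets the material, when, or how much.

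**The content.** For IC participants, "the research staff will provide participants with a weekly learning module that will consist of presenting information on relevant health-related topics", for example about the conditions that made them eligible.

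**The design.** Section 4.1: "After the staggered baseline periods, all participants will receive EFT intervention". Section 5.1: "participants will be randomized to a 6 week, 8 week, or 10 week staggered baseline periods followed by 4-8 weeks of Episodic Future Thinking (EFT"). The Section 1.0 summary and the intervention description in Section 6.1 mention EFT only. The Section 13.2 timetable has three groups, defined by baseline length alone.

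**The conflicting sentence.** Section 12.1 also says that at intervention meetings "participants will either complete EFT or IC activities, dependent on group assignment". EFT/IC wording continues into Section 12.3.

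**The contrast.** Section 12.1 on baseline: "All participants complete a 6-week baseline in which they will use the MEMS bottles", followed by adherence checks. Sections 19.1 and 19.2 plan a graphical analysis and an assessment of the change from baseline to treatment across the three staggered replications.

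**The concern.** The permission exists to equalise knowledge between two groups. With no second group it has nothing to equalise, and its effect reverses: it allows a second, possibly active component to enter at the phase change that defines the treatment effect. Aim 1 credits any rise in adherence to EFT, and Section 4.1 wants effect sizes from this pilot for a later grant application. If education raised adherence, that rise would be carried forward as an EFT effect. If only some participants received it, the replications would not be testing the same intervention.

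**Working it through.** **1. Which design governs.** Sections 1.0, 4.1, 5.1, 6.1 and 13.2 agree on EFT for all. The EFT/IC wording in Sections 12.1 and 12.3 assumes two intervention groups. Both cannot be true, and the answer decides the point:

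- If an IC group exists, sharing the information balances education between groups.
- If all receive EFT, the only contrast is within person, and sharing the information adds something to the treatment phase that baseline lacked.

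**2. Timetable check.** Section 13.2 places the intervention in weeks 7 to 14, 9 to 14 and 11 to 14, that is 8, 6 and 4 weeks. Total hours = 0.5 + 2.5 + weeks × (0.2 + 0.58) + 2 × 2:

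- 6-week baseline: 7 + 8 × 0.78 = 13.24
- 8-week baseline: 7 + 6 × 0.78 = 11.68
- 10-week baseline: 7 + 4 × 0.78 = 10.12

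All three match the stated totals. The timetable is built on three baseline lengths, with no IC group.

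**3. What the contrast estimates.** Write adherence of person i in week t as person effect + week effect + β·EFT + γ·Education. Suppose education, where given, starts with EFT, and a share p of participants receives it. The average change from baseline to treatment, net of week effects, is then β + p·γ. The bias in the EFT effect is p·γ. The documents allow any p from 0 to 1 and give no γ.

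**4. Can staggering separate β from γ?** I checked the rank of the design matrix with person effects, week effects, an EFT indicator and an education indicator. Assumptions: 12 participants (the upper end of the 10-12 randomization goal in Section 7.1), four per baseline length, weeks 1 to 14.

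| Delivery of education (assumed) | EFT effect separately estimable? |
|---|---|
| Starts with EFT, everyone | No: the two indicators are identical |
| Starts with EFT, half of participants | Yes, but only through the split between 6 given it and 6 not |
| Starts at week 3, everyone (within baseline) | Yes |
| Nobody | Yes |

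Staggering protects against calendar-time effects. It does not protect against a component that moves with the phase change. In the half-and-half case, separation rests on a small, non-randomized split.

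**5. Could it be repaired in analysis?** The split would have to be known. Section 12.2 lists cue recordings, session recordings, cognitive and adherence measures, and background data, but not receipt of health information. Session recordings might show teaching in a session; they would not show a pamphlet or a web page read at home. Section 19.1 plans no adjustment.

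**The case against.** The best defence is that this is dead text. With no IC group, no IC participant is provided anything, so the permission has no referent. Section 6.1 contains no education, and the real defect is the unreconciled two-group wording. Much of this stands: the point depends on resolving that contradiction and should be handled with it. But the permission sits in the current procedures, and the website clause is a separate route for the same content.

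A second defence is that education may do little here. Section 4.1 describes participants whose main difficulty is remembering, and Section 8.1 requires motivation or intent to comply better. That stands as a reason to expect a small effect, not as a reason to leave the component uncontrolled.

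Third, reminders and walk-through calls also begin with the intervention, so removing education does not isolate EFT. That is correct. For a pilot, describing the effect as that of a package is legitimate, provided the package is fixed and stated.

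A reader might go further and infer that staff will choose which participants get the full weekly modules during the EFT phase. The text does not say so. It says that the information may be given, sets no rule or timing, and does not assign EFT participants the modules or quizzes. Delivery alongside EFT is an inference from the placement under Intervention Sessions.

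**Conclusion.** The concern holds under the all-EFT design. The protocol permits a second component to start with EFT, its contribution could not be separated from EFT if everyone received it, and receipt is not among the listed data. The bias is possible, not certain. A reader might put a figure in percentage points on it by multiplying an assumed share by an assumed effect. The documents support neither input, and zero is within the range because delivery is optional. All that follows is that the bias lies between nothing and the full effect of the material.

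Two assumptions carry the conclusion: that Sections 1.0, 4.1, 5.1 and 13.2 state the intended design, and that material given under the intervention text would not have been given in baseline. If a concurrent IC group were really intended, the permission would balance the groups and this point would fall away.

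**What to change.** Reconcile the EFT/IC wording in Sections 12.1 to 12.3 with the all-EFT design. In the same amendment, delete the health-information permission and the matching website clause, or state that the material is withheld until T3 is complete.

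If the sponsor wants to keep it, deliver it identically to all participants, add receipt to the data list in Section 12.2, and describe the result as the effect of EFT plus education.

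Giving the material to everyone at T1 would also keep it from starting with EFT, but it is a weaker choice. It could raise baseline adherence or produce a rising trend. Under the baseline rules in Section 12.1, a rising trend delays entry to the intervention, and participants not below 80% by week 10 are dismissed. With a goal of 10-12 randomized, few can be lost.

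The cost is a short amendment, though more than one sentence because the IC wording runs through several subsections. Withholding also means participants receive the information later or, if the clauses are deleted, not through the study; Section 24.1 lists learning about their health as a possible benefit. Reminders and calls would still begin with EFT and should be acknowledged when the effect is interpreted.

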13.0 Study Timelines*

13.1 Describe the anticipated duration needed to enroll all study subjects.

Response:

We anticipate it will take up to 6 months to recruit all participants.

13.2 Describe the duration of an individual subject's participation in the study. Include length of study visits, and overall study follow-up time.

Response:

Participants will be in the study for approximately 15 weeks, from the time of the initial online screening survey is completed, and until the final study assessment is completed. An outline of the approximate duration of each session type and corresponding study week is provided below.

Group	Session Type	Session Duration (Hours)	Study Weeks
6-Week	Online Screen	0.5	0
	Assessment (T1)	2.5	1
	Intervention Phone Calls	0.2	7 to 14
	Intervention Sessions	0.58	7 to 14
	Assessments (T2, T3)	2	6, 15
	Total Time	13.24	
8-Week	Online Screen	0.5	0
	Assessment (T1)	2.5	1
	Intervention Phone Calls	0.2	9 to 14
	Intervention Sessions	0.58	9 to 14
	Assessments (T2, T3)	2	8, 15
	Total Time	11.68	
10-Week	Online Screen	0.5	0
	Assessment (T1)	2.5	1
	Intervention Phone Calls	0.2	11 to 14
	Intervention Sessions	0.58	11 to 14
	Assessments (T2, T3)	2	6, 15
	Total Time	10.12	

13.3 *Describe the estimated duration for the investigators to complete this study (i.e. all data is collected and all analyses have been completed).*

Response:

We anticipate the study will take approximately 1 year to complete.

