completing quizzes to assess mastery of educational materials, with multiple versions of quizzes on each module available to account for those who need or desire additional practice. The website will also contain password protected sections that are for internal use by study personnel. The website will not contain protected health information.

Because use of the EMI is not incentivized in any way, staff will conduct walk-throughs by phone with the participant to ensure that the participant is using the intervention outside of the lab. These walk-through calls will consist of guiding the participant through the use of their EFT/IC cues; calls will last about 15 mins, and will be scheduled with participant. Check-ins (practice and reminders) may occur both during the intervention weeks and during the study follow-up period prior to the final assessment. Participants may also receive reminder texts/email/or phone calls to use their EFT/IC cues.

During CDC recommended travel restrictions due to flu, respiratory illness or coronavirus, we are enacting preventative measures to ensure both participants and employees limit exposure.

- (1) Participants will be asked during reminder calls/emails/text messages/scheduling contacts questions regarding their health and their child's health before in-person meetings. This language can be used in any contact of scheduling participants such as, in-person or phone, email, text, letter,etc

Example of .."With the current situation involving the flu, respiratory illnesses, and the coronavirus, the Imagine to Remember Study team are enacting some preventive measures to keep everyone healthy. The Imagine to Remember Study Team wants to ensure the safety of all staff and our participants. While we understand that there are areas with confirmed cases of the virus and your area may or may not be affected, we would like to help prevent the possible spread by asking a few questions prior to your appointment."

1. -"Have you or your child traveled in the last 14 days? If so, where? (effected confirmed areas are changing daily)
2. -Are you or your child experiencing or showing any symptoms related to the flu, or other respiratory illnesses such as the coronavirus, including fever, cough or shortness of breath?

If new information about symptoms is found, we will follow CDC guidelines/recommends

<https://www.cdc.gov/coronavirus/2019-ncov/about/symptoms.html>

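### The section 13.2 table places T2 for the 10-week group at week 6, five weeks before its EFT starts, against one week in the other two groups

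*Combined protocol and SAP*

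**What the plan says.** The table in section 13.2 gives each group three assessments. T1 is in week 1 and T3 in week 15 for everyone. T2 is in week 6 for the 6-week group, week 8 for the 8-week group and week 6 for the 10-week group, whose row reads "Assessments (T2, T3) 2 6, 15" (session type, hours, study weeks). The 6-week group has the same row. EFT runs in weeks 7 to 14, 9 to 14 and 11 to 14 respectively.

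Section 12.1 says of the longest baseline that "those in the 10-week will complete four more weeks of baseline prior to the intervention", counting from week 6. It also has a common contact: "At week 6, all participants will attend an in-person lab session to assess their adherence levels". The stated content of that contact is MEMS data and pill counts. Before EFT there is a further check: "Participants must be considered stable based on their pill counts to continue to the intervention period". The same paragraph adds: "If a participant was assigned to a group but is not stable during that time period, they will be assigned to the next group".

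DD and PM belong to the assessment sessions in section 12.1, with this qualification: "Some of these tasks may only be administered in certain assessment sessions (e.g., the initial and/or final". Section 4.1 describes the timing differently: "At an initial baseline session, post-intervention, and follow-up, participants will complete measures of working memory, lab-based PM, and DD". Section 27.1 pays for three assessment sessions.

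**The concern.** In two of the three rows T2 sits in the last baseline week, where it gives a measurement just before treatment. In the 10-week row it does not, although section 12.1 keeps that group in baseline through week 10.

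Aim 2 asks whether EFT changes DD and PM. Section 4.1 says the pilot is meant to supply effect sizes for a later grant, and section 19.2 treats the three baseline lengths as replications. If staff work from the table, one of those replications has no DD or PM value at the end of baseline, and the value cannot be recovered later. A T2-to-T3 change in that group would cover a stretch of untreated time that the other two groups do not have.

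**Working it through.** **Inputs.** From the section 13.2 table: T1 in week 1; T2 in weeks 6, 8, 6; first EFT week 7, 9, 11; last EFT week 14; T3 in week 15; hours 0.5 (screen), 2.5 (T1), 0.2 (call), 0.58 (session), 2 (each of T2 and T3). From section 7.1: a goal of at least 10-12 randomised.

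**The table's own totals.** Hours = 0.5 + 2.5 + EFT weeks × (0.2 + 0.58) + 2 × 2.

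- 6-week group: 7 + 8 × 0.78 = 13.24, as stated.
- 8-week group: 7 + 6 × 0.78 = 11.68, as stated.
- 10-week group: 7 + 4 × 0.78 = 10.12, as stated.

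All three reproduce. None depends on the week in which T2 is held, so the totals cannot show which week was intended.

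**Intervals in elapsed weeks.**

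| Interval | 6-week | 8-week | 10-week | 10-week, T2 at week 10 |
|---|---|---|---|---|
| T1 to first EFT week | 7 − 1 = 6 | 9 − 1 = 8 | 11 − 1 = 10 | 10 |
| T2 to first EFT week | 7 − 6 = 1 | 9 − 8 = 1 | 11 − 6 = 5 | 11 − 10 = 1 |
| T2 to T3 | 15 − 6 = 9 | 15 − 8 = 7 | 15 − 6 = 9 | 15 − 10 = 5 |

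In the 10-week group, 10 − 6 = 4 of the 9 weeks between T2 and T3 are untreated baseline weeks. In the other groups T2 is already in the last baseline week, so the corresponding figure is 0.

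**People affected.** Equal allocation is an assumption, since no ratio is given: 10/3 = 3.3 to 12/3 = 4. The number rises if the stability rule in section 12.1 moves participants into the 10-week group.

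**Does the common week-6 contact explain the entry?** Section 12.1 describes it as an adherence check, and under the COVID-19 alternative it is only a collection of the MEMS cap. If T2 had been tied to it, the 8-week group's T2 would also be in week 6, but the table has week 8.

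**Does another section supply the missing value?** No. Section 4.1 lists no end-of-baseline assessment, and section 12.1 lets some tasks be given only at certain sessions.

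**The case against.** The strongest reply is that the wrong cell may be blamed. Everyone has a week-6 contact, MEMS data and pill counts are also part of an assessment session, and two of the three rows say week 6. On that reading the 8-week entry is the odd one. This cannot be excluded, and a copying slip from the 6-week row cannot be proved either. But it still leaves the rows inconsistent, and if T2 were at week 6 throughout, the 8-week group would lose its end-of-baseline value too (9 − 6 = 3 weeks before EFT).

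A second reply is that the table is offered as an approximate outline in answer to a question about participation time, while section 12.1 is the procedural blueprint. That is fair, but section 12.1 gives no week for T2, so the table is the only source for it, and a four-week departure from the pattern of the other rows is not rounding.

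Third, the consequence is limited. This stands. T1 and the early T2 both precede EFT, section 19 names no DD or PM contrast, and this is a small pilot.

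Fourth, the other groups are not secure either. This also stands. Under section 4.1 no group has a value just before EFT, and under section 12.1 neither DD nor PM is guaranteed at T2 in any group. A reader might infer from the table that only the 10-week group is exposed; the documents do not support that.

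**Conclusion.** The inconsistency is real: T2 is 5 weeks before EFT in the 10-week group and 1 week before it in the others. Followed as written, about 3 to 4 people (equal allocation assumed) have no assessment at the end of baseline, and their T2-to-T3 change carries four extra untreated weeks of possible drift or practice. The documents give no figure for the size of that. Severity is minor to should-fix: the effect is confined to Aim 2, but correction is cheap beforehand and impossible afterwards.

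Some stronger readings do not hold:

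- A reader might infer that the group has no pre-EFT value, or that a planned test is biased. It has values at weeks 1 and 6, and no such test is planned. DD and PM are point measures, so an early T2 does not dilute an EFT effect.
- A reader might infer that section 12.1 implies a session after T3. Its wording is "during the study follow-up period prior to the final assessment", which places the follow-up period before the last assessment. Only section 4.1 conflicts with the table.
- A reader might infer from section 12.3, which allows visualisation during DD and before Virtual Week rounds without naming the session, that testing must be uncued throughout. Whether Aim 2 concerns cued or uncued performance is a measurement choice the documents leave open. What matters is that sessions to be compared use the same condition.

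**What to change.** 1. In section 13.2, define T2 as the last week of the baseline the participant actually completes, held together with the pre-EFT stability check. That is week 10 for the 10-week group, and later than first assigned if the stability rule moves a participant.
2. In section 12.1, state that DD and the PM tasks are given at T1, T2 and T3.
3. Reconcile section 4.1 (initial baseline, post-intervention, follow-up) with the three-session table. If a measurement after T3 is wanted as well, it is a fourth session and must appear in sections 13.2 and 27.1, at $35 per person: 10 × $35 = $350 to 12 × $35 = $420. If it is not wanted, amend section 4.1.
4. Separately, in section 12.3, state which sessions use visualisation, and keep the condition the same in any sessions that are compared.

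**Cost.** One table cell and wording in sections 4.1, 12.1 and 12.3. The 10-week total stays at 10.12 hours. The 10-week group may need one extra contact if T2 was meant to be combined with the week-6 check, although holding it with the stability check may avoid this. Fixing the task set removes the flexibility section 12.1 now allows. T2-to-T3 intervals become 9, 7 and 5 weeks and so vary with EFT duration (8, 6 and 4 weeks), whereas the present entry gives 9 weeks in both the 6- and 10-week groups. Any Aim 2 comparison should be described with that in mind.
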